3. INTERVENTION

3.1 INTERVENTION OVERVIEW

The study will randomize 45 HIV-positive persons with past year heavy alcohol consumption (by NIAAA definition of at risk drinking) and chronic pain (defined as bodily pain of moderate to severe intensity lasting for ≥ 3 months). Existing Russia ARCH participants, and past St PETER, LINC-II, and PETER PAIN participants will be offered to be screened for this study. Recruitment beyond First St. Petersburg Pavlov State Medical University (PSMU) will occur at local NGOs, Russia ARCH network hospitals including the major clinical HIV and addiction hospitals. Some participants may be screened over the phone, but all interested potential study participants will ultimately be invited for an in-person screening of eligibility at PSMU. After eligible participants are consented and enrolled, the RA will complete screening for eligibility by conducting a rapid HIV test for non-ARCH participants, a urine drug test, blood draw for

AST/ALT and creatinine testing, and testing all women for pregnancy (urine). Once AST/ALT and creatinine results are received, participants will be notified by phone and if eligible, will be invited to return to Pavlov for their baseline visit.

At the baseline visit, participants will be administered the naloxone challenge and observed for signs of opioid withdrawal for 20 minutes. Naloxone blocks the effects of opioids. It works only if it is injected and lasts about 30 minutes. It is used in hospitals and by emergency services to reverse the effects of a heroin or other opioid overdose. It will cause withdrawal if injected into someone who is currently physically dependent on opioids and will be administered to make sure that the participant is not physically dependent on heroin or other opioids before s/he is given oral naltrexone. The naloxone challenge will only be administered if the information the participant provides to the staff indicates that s/he is not physically dependent on heroin or other opioids and if his/her urine drug test is negative. The challenge will be done by administering 0.8-mg naloxone slowly intramuscularly. The participant will be observed by a research assessor for signs of withdrawal for 5-20 minutes. If the participant experiences withdrawal after the naloxone test, his/her symptoms may be treated with 150mcg clonidine or 2mg of phenazepam orally and will go away in 45-60 minutes. As withdrawal symptoms precipitated by naloxone typically resolve within 20 minutes without treatment, use of these medications will be decided on a case-by-case basis by the treating Russian physician-investigator.

In the consent form, participants will be alerted that they may experience the following side effects if they need to be treated with clonidine or phenazepam:

The most frequent side effects (which appear to be dose-related) of clonidine are dry mouth, drowsiness, dizziness, constipation and sedation. The most frequent side effects of phenazepam are drowsiness, sedation, muscle weakness, and ataxia. These side effects generally decrease on continued administration and are a consequence of CNS depression.

The participant will not be started on the study medication until s/he passes a naloxone challenge, which means that s/he has no signs or symptoms of opioid withdrawal after naloxone is administered.

If the participant fails the naloxone challenge, s/he will be invited to come back within a week to repeat the challenge. Participants who pass the naloxone challenge will then complete the study assessment, cold-pressor testing and be randomly assigned to either low-dose naltrexone, gabapentin, or placebo. Study medication will be provided by trained physicians, who will instruct participants in proper medication administration and adherence.

Study participants, investigators, staff, and physicians administering the medications will be unaware of specific group assignment.

Participants will be treated for 8 weeks, and observed for 4 weeks post-treatment. Outcomes (pain severity and interference (BPI), biomarkers IL-6, 1 β , IL-10, and TNF- α , cold pain tolerance, percentage of past month heavy drinking days, CD4 cell count, and HIV viral load) will be evaluated at the end of treatment.

Throughout the course of the study, participants will be expected to come in for eight in-person assessments. The schedule of study in-person visits/assessments are as follows: baseline, 1, 2, 4, 6, 7, 8, and 12 weeks. At week 4, we will assess for medication tolerability, discontinuation, treatment side effects, self-reported adherence to intervention medications, and pain (BPI) only. At week 8, we will assess pain (BPI), biomarker IL-6, IL-1 β , IL-10, and TNF- α levels, cold pain tolerance using cold-pressor, pain interference, percentage of past month heavy drinking days, and HIV control (CD4 cell count & HIV viral load). At week 12 (post-treatment), there will be an assessment of pain (BPI) and cold-pressor test to assess whether pain reverts back to pre-treatment levels. Weeks 1, 2, 6, and 7 will be short visits, at which a brief assessment of tolerability, side effects, and adherence will occur, and we will ensure that participants have their medications (e.g. have not been lost or stolen).

Visits will be preceded by phone/text reminders to the participant or alternate contacts.

The text message will read: "This is a reminder that your visit to Pavlov Medical University is scheduled for____at___. Please reply to confirm or call [name] to reschedule."

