2.3 STUDY DESIGN

This is a randomized, double-blinded, 3-arm study of 45 participants with HIV, chronic pain (defined as any bodily pain of moderate to severe intensity lasting for ≥3 months), and past-year heavy alcohol use, defined by NIAAA criteria. The 45 participants will be randomly assigned to either naltrexone, gabapentin, or placebo, using permuted blocks, to ensure equal numbers in each arm. Patients and research staff will be blinded to randomization. Participants will be treated for 8 weeks, and then assessed for an additional 4 weeks post-treatment.

The study design and schedule for study visits and assessments is depicted in Figure 1. After consent and enrollment, participants will be randomly assigned to receive either low-dose naltrexone, gabapentin, or placebo. Participants will be randomized using permuted blocks, to ensure similar numbers within each arm. Patients and research staff will be blinded to randomization. Participants will be given 2 weeks of medication at baseline, 2-weeks, 4-weeks, and 6-week visits, with instructions to bring pill packs/leftover medications to the following visit. The schedule of study visits is as follows: baseline (pre-treatment), week 4 (on treatment), week 8 (on treatment), week 12 (post-treatment). At the 8 week visit, all assessments will occur (see Section 5). At week 4, we will assess for medication tolerability, discontinuation, treatment side effects, self-reported adherence to intervention medications, and pain (BPI) only. At week 12 (post-treatment), there will be an assessment of pain (BPI) and cold-pressor test to assess whether pain reverts back to pre-treatment levels. Weeks 1, 2, 6, and 7 will be short visits at which time a brief assessment of tolerability, side effects, and adherence will occur, and we will ensure that participants have their medications (e.g. have not been lost or stolen).

Figure 1: Study Design (UH3 Phase)

Page 5 of 44

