	Compensation	compensation.
	Window	30 days after completion of screener
		3 weekly attempts; at final attempt
	Final attempt	provide full compensation.
Timing of		If blood draw is not successful,
	blood draw	proceed to assessment.
Follow up*		Given partial (1/2) compensation
(8-week visit	Compensation	for completion of assessment.
only)		30 days after completion of
Office	Window	assessment.
		4 weekly attempts; at final attempt
	Final attempt	provide full compensation.

3.6.D. COLD-PRESSOR TESTING

The cold-pressor test (CPT) is an experimental model that assesses cold pain threshold and tolerance. It is a research paradigm that has been used by researchers for decades, and has been utilized to measure enhanced sensitivity to cold pain (hyperalgesia). The investigators will use an automatic cooling water bath that keeps a constant temperature of 0–2 degrees Celsius. Participants are instructed to place their dominant arm in the cold water bath so that ice water covers the hand and approximately 10 cm of the forearm, to verbally indicate when they first perceive pain and, to rate their pain on a scale of 0-100 at its very worse, and when they can no longer tolerate the ice bath, to remove their arm from the water. The time from submersion to those events will be measured using a stopwatch. Cold pain threshold is measured as number of seconds to the initial perception of pain, and cold pain tolerance is measured as seconds until withdrawal of hand. Trials will be discontinued at 3 minutes since after this time pain severity diminishes as numbness sets in. This data will be collected at baseline, week 4, week 8, and week 12. Participants will be requested to refrain from over the counter analgesic use (non-steroidal anti-inflammatory pain medications or acetaminophen) for 24 hours prior to the study visit.

3.6.E. DAILY PAIN DIARY

Participants will be asked to keep a daily written record ("daily diary") of pain severity, medication adherence, and alcohol use.

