4.4 VISIT FLOW

Pre-screen (optional):

• Screening questions administered over the phone

Screening visit:

- Screening Questions
- Informed Consent and Enrollment

- Conduct HIV, urine drug test, draw blood for AST/ALT and Creatinine testing (if recent test result not provided), and pregnancy testing
- Compensate participant, collect locator/contact information and check contact phone numbers
- Schedule return visit, if eligible
- Provide resource document, appointment reminder card

Baseline visit:

- Review and update locator/contact information, verifying new numbers, as necessary
- Conduct urine drug testing and pregnancy testing
- Administer naloxone challenge
- Administer assessment questionnaire
- Assess baseline symptoms
- Randomize participant
- Conduct cold-pressor test
- Draw blood for biomarker, CD4, and HVL testing
- Introduce study medication and instructions and develop an adherence plan
- Provide study medication
- Observe participant for 30 minutes after the participant takes the first dose
- Compensate participant; provide appointment reminder card, participation card, daily diary, and schedule next visit

1-, 2-, 6-, and 7-week medication visit:

- Review and update locator/contact information, verifying new numbers, as necessary
- Collect a urine sample to check for pregnancy (females only)
- Draw blood for ALT/AST testing, if indicated (6-week only)
- Administer a brief assessment of tolerability and side effects
- Assess medication adherence
- Provide study medication (1-week, 2-week, 4-week, 6-week visits)
- Compensate participant and schedule next visit

4-, 8-, and 12-week full study visit:

- Review and update locator/contact information, verifying new numbers, as necessary
- Collect a urine sample to check for pregnancy (4-week only, females only)
- Assess medication adherence
- Administer assessment questionnaire
- Conduct cold-pressor test
- Draw blood for ALT/AST (4-week, and 6-week if indicated only) and biomarker, CD4, and HVL (8-week only) testing
- Provide study medication (4-week only)
- Compensate participant and schedule next visit (4- and 8-week only)

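### The baseline cold-pressor test follows a naloxone injection with no minimum interval, while no later test follows an injection; the week-12 return-to-baseline reading is exposed, the between-arm comparison is not

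*Combined protocol and SAP*

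**What the plan says.** Section 3.1 (Intervention Overview) describes the challenge given at the baseline visit: "The challenge will be done by administering 0.8-mg naloxone slowly intramuscularly". On its action the section says "Naloxone blocks the effects of opioids" and "It works only if it is injected and lasts about 30 minutes". It gives the observation period once as 20 minutes and once as 5 to 20 minutes; section 3.3.D repeats both. Everyone must pass before dosing: "The participant will not be started on the study medication until s/he passes a naloxone challenge". The order is then "Participants who pass the naloxone challenge will then complete the study assessment, cold-pressor testing and be randomly assigned".

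The baseline list in section 4.4 (Visit Flow) also puts "Administer naloxone challenge" ahead of the questionnaire, the baseline symptoms and the cold-pressor test. The schedule in section 3.5 marks the challenge at baseline only. On the cold-pressor test, section 3.6.D says "This data will be collected at baseline, week 4, week 8, and week 12". It asks participants to avoid over-the-counter analgesics for 24 hours beforehand and does not mention naloxone.

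Section 2.3 gives the purpose of the week-12 visit: "there will be an assessment of pain (BPI) and cold-pressor test to assess whether pain reverts back to pre-treatment levels".

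**The concern.** The trial tests whether a drug that blocks opioid receptors changes pain, and cold pain tolerance is one of its secondary outcomes. Yet the reference value for that outcome is taken after an injection of another opioid antagonist, under a condition that no later visit repeats. The protocol controls recent over-the-counter analgesic use before the test but not the antagonist it gives at the same visit.

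If naloxone alters cold pain tolerance for the minutes it acts, the baseline is not a clean pre-treatment value. Each participant's change from baseline would then mix any treatment effect with the wearing off of naloxone. The week-12 question is the most exposed, because it compares people with their own baseline and randomisation gives it no protection.

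**Working it through.** The plan gives no figure for the interval, the questionnaire length or any naloxone effect, so there is nothing of its own to reproduce. The check has three parts.

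**1. Timing**

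Inputs from section 3.1: duration of action about 30 minutes; observation 5 to 20 minutes.

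Action remaining when the assessment starts = duration − observation:
- after 20 minutes of observation: 30 − 20 = 10 minutes
- after 5 minutes of observation: 30 − 5 = 25 minutes

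The questionnaire comes next. If it takes q minutes, the action remaining at the cold-pressor test is at most max(0, 30 − observation − q). Overlap therefore needs q below 10 minutes in the first case and below 25 in the second. The documents do not state q.

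**2. Effect on the estimates**

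Let B be the baseline value without naloxone, S the shift naloxone causes, and Y the follow-up value. Observed change is Y − (B + S).
- Within an arm: mean observed change = mean(Y − B) − mean(S). A mean shift of d moves the arm's change by −d.
- Between arms, for a common shift: (Y1 − B1 − S) − (Y0 − B0 − S) = (Y1 − B1) − (Y0 − B0). The shift cancels.
- The shift need not be constant or additive. Naloxone precedes randomisation and the first dose, so the expected observed baseline is the same in every arm whatever form the response takes. The difference in mean change is therefore unbiased.

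A simulation illustrates this, with 13 per arm and 20,000 runs. The assumptions are a mean tolerance of 60 s, an SD of 30 s, a within-person correlation of about 0.6 and a true effect of 10 s; none comes from the documents.

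| Baseline shift (s) | Between-arm difference (s) | Placebo within-arm change (s) |
|---|---|---|
| 0 | 9.9 | 0.1 |
| −5 | 10.0 | 5.0 |
| −10 | 10.1 | 10.0 |
| −20 | 10.0 | 20.0 |

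The negative direction is also an assumption; a positive shift would act in reverse.

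**3. Precision**

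Suppose the naloxone response varies between people with SD s, independently of the rest of the change score, which has SD σ. With the sample size fixed, the confidence interval widens by √(σ² + s²)/σ − 1.

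| s (s) | σ = 30 s | σ = 50 s |
|---|---|---|
| 5 | 1.4% | 0.5% |
| 10 | 5.4% | 2.0% |
| 20 | 20.2% | 7.7% |

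For example, with s = 10 and σ = 30: √(900 + 100)/30 − 1 = 31.62/30 − 1 = 5.4%. Both SDs and the independence are assumptions.

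**The case against.** The strongest reply is that little of consequence is exposed, and most of it stands.

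- **Primary outcome.** A reader might infer that all baseline pain measures are contaminated. Section 2.2 defines the primary BPI outcome over the past week, and heavy drinking is a 30-day recall. An injection minutes earlier has little scope to change either. The items of the modified BPI are not listed, so an effect on a current-pain item would be conjecture.
- **Treatment comparison.** A reader might infer bias between arms, or absence of bias only if the naloxone effect is additive and equal. Neither follows, as shown in the working. Section 4.4 lists the cold-pressor test after randomisation, but it is still after naloxone and before the first dose.
- **Design of the next trial.** A reader might infer that the pilot's main product is damaged. Sections 2.7.A and 8.1 make between-arm differences with confidence intervals the planned product. Section 8 sets out no within-arm test and no week-12 analysis.
- **Overlap.** A reader might take it as established. The baseline battery in section 5.1 covers 14 listed topics, including a 30-day drinking calendar, and may well outlast the remaining 10 to 25 minutes. Overlap is possible, not shown.
- **A naloxone effect at all.** The trial studies eight weeks of daily oral naltrexone. The documents nowhere say that one injection alters cold pain tolerance in people screened negative for opioids.
- **Opioid blockade only at baseline.** The naltrexone arm is assigned an opioid antagonist during treatment, so what is unique to baseline is the injection.
- **Blood draw.** Nothing in the documents supports moving it on account of naloxone.

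What the reply does not remove is that no interval is set, and that the week-12 purpose in section 2.3 depends directly on the baseline value.

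**Conclusion.** The point holds in a narrow form. The baseline cold-pressor test may fall inside the stated 30-minute naloxone window, and no later test follows an injection. Three things are exposed: within-arm cold-pressor change, the week-12 comparison with the pre-treatment level, and possibly the precision of this one secondary outcome.

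The documents do not give the size. A mean baseline shift of d seconds would carry through in full to each arm's change at weeks 4, 8 and 12, and not at all to the between-arm difference in mean change. Under the assumed SDs, intervals would widen by 0.5% to 20%, and the upper end needs the least favourable combination. If the questionnaire always outlasts naloxone, the effect on the test should be small on the protocol's own account of how long naloxone acts.

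This is a cheap improvement. It gives no reason to doubt the primary outcome or the randomised comparison.

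**What to change.** In sections 3.1 and 4.4, adopt one of two orders.

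1. Do the baseline questionnaire and then the cold-pressor test before the naloxone challenge, with randomisation and first dose still after it. Keeping the questionnaire ahead of the test preserves the order used at follow-up visits. The cost is that a participant who fails the challenge and returns may have to repeat these measures.
2. Keep the present order, and require the cold-pressor test to start no sooner after the injection than the naloxone duration the protocol itself states. Record the clock times of the injection and the test. The cost is a short wait, or none if the questionnaire already takes that long.

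Neither adds a procedure or alters the challenge itself.

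The same edit should settle inconsistencies in the baseline sequence:
- Section 3.1 puts the cold-pressor test before randomisation; section 4.4 lists it after.
- Section 3.6.C requires the baseline blood draw before the assessment; section 4.4 lists it after the questionnaire and the cold-pressor test.
- Sections 3.1 and 3.3.D each give the observation period in two ways, and these need to be reconciled.

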3.2 RANDOMIZATION

After consent and enrollment, participants will be randomly assigned to either low-dose naltrexone, gabapentin, or placebo with a 1:1:1 allocation ratio using permuted blocks to ensure equal numbers in each arm. Participants and research staff will be blinded to randomization arm.

Study medications will be obtained in St. Petersburg and delivered to the study pharmacist at PSMU prior to initiation of recruitment processes. The study pharmacist will deliver a supply of packaged boxes of study medication labeled with the group assignment to the study team.

Following completion of the baseline assessment, the RA will be directed to the electronic randomization screen in REDCap, which, once submitted, automatically assigns the participant to a randomization group. The RA then retrieves the pack of study medication from the identified group, labels the pack with the participant study ID, and enters the group number into REDCap, thus linking the two numbers.

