Please note that these side effects were reported among people taking 50mg of naltrexone. This study will use low dose naltrexone (4.5mg) and side effects are expected to be milder. In order to help prevent these adverse effects, participants will be instructed not to take more medication than what is provided by the study. Study clinicians will also be monitoring for signs of naltrexone overdose. These adverse effects are not expected to be likely.

3.3.B. GABAPENTIN

Participants randomized to this group will receive gabapentin for 8 weeks.

Gabapentin dosing will start on the day of the baseline visit after successful passing of the naloxone challenge. If the participant does not pass the naloxone challenge, he/she will be brought back within a week to try again.

Participants will be instructed to take the medication from one to three times daily for 8 weeks. Medication will be packaged in pill boxes. Participants will receive 1 box of 7 capsules and 1 box of 21 capsules at baseline (14 days worth of medication), at the 1-week visit participants will receive 1 box of 42 capsules, at the 2-week visit participants will receive 2 boxes of 42 capsules, at the 4-week visit participants will receive 2 boxes of 42 capsules; at the 6-week visit participants will receive 1 box of 33 capsules.

Participants randomized to the gabapentin arm begin on a dose of 300 mg daily (300 mg qd). In week 2, participants will take 300 mg of gabapentin three times daily. In week 3 the dose will be titrated up to 1800 mg daily (300 mg+300 mg tid) will remain on the dose until week 8, when they will be tapered back down to 900 mg daily (300 mg tid). In week 8, in days 1-4 participants will take 1800 mg daily (300 mg+300 mg tid); in days 5-7, participants will take 900 mg daily (300 mg of gabapentin three times daily). Gabapentin will only be titrated up as tolerated by the participant. Participants will be monitored regularly for side effects and medication tolerability (weeks 1, 2, 4, 6, and 7) If a participant experiences adverse effects while on medication, the participant's dose will be reduced down to the previous dose (or to a lower dose that the participant can tolerate). Research Assessors in this study are all trained addiction psychiatrists, with experience in clinical trials and adverse event monitoring.

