 - Days 1-4 (6 capsules/day): 1 placebo to be taken with 4.5 mg naltrexone qd, 2 placebo capsules to be taken bid
 - o Days 5-7 (3 capsules/day): 4.5 mg naltrexone qd, 1 placebo capsule bid
- Participants will receive 1 box of 7 capsules and 1 box of 21 capsules at baseline (14 days' worth).
- Participants will receive 1 box of 42 capsules at week 1 (7 days' worth).
- Participants will receive 2 boxes of 42 capsules at week 2 (14 days' worth).
- Participants will receive 2 boxes of 42 capsules at week 4 (14 days' worth).
- Participants will receive 1 box of 33 capsules at week 6 (7 days' worth).

Gabapentin:

- 7 capsules/box, 1 capsule/day (Week 1)
 - Week 1: 300 mg qd (300mg total)
- 21 capsules/box, 3 capsules/day (Week 2)
 - o Week 2: 300 mg tid (900 mg total)
- 42 capsules/box, 6 capsules/day (Week 3-7)
 - Weeks 3-7: 2 capsules of 300 mg tid (1800 mg total)
- 33 capsules/box (Week 8)
 - o Days 1-4 (6 capsules/day): 2 capsules of 300 mg tid (1800 mg total)
 - o Days 5-7 (3 capsules/day): 300 mg tid (900 mg total)
- Participants will receive 1 box of 7 capsules and 1 box of 21 capsules at baseline (14 days' worth).
- Participants will receive 1 box of 42 capsules at week 1 (7 days' worth).
- Participants will receive 2 boxes of 42 capsules at week 2 (14 days' worth).
- Participants will receive 2 boxes of 42 capsules at week 4 (14 days' worth).
- Participants will receive 1 box of 33 capsules at week 6 (7 days' worth).

Placebo:

- 7 capsules/box, 1 capsule/day (Week 1)
 - o Week 1: 1 placebo capsule qd
- 21 capsules/box, 3 capsules/day (Week 2)
 - Week 2: 1 placebo capsule tid
- 42 capsules/box, 6 capsules/day (Week 3-7)

- Weeks 3-7: 2 placebo capsules tid
- 33 capsules/box (Week 8)
 - o Days 1-4 (6 capsules/day): 2 placebo capsules tid
 - o Days 5-7 (3 capsules/day): 1 placebo capsule tid
- Participants will receive 1 box of 21 capsules and 1 box of 42 capsules at baseline (14 days' worth).
- Participants will receive 1 box of 42 capsules at week 1 (7 days' worth).
- Participants will receive 2 boxes of 42 capsules at week 2 (14 days' worth).
- Participants will receive 2 boxes of 42 capsules at week 4 (14 days' worth).
- Participants will receive 1 box of 33 capsules at week 6 (7 days' worth).

Medication boxes will also be labeled. The medication labels will contain the following information:

FOR CLINICAL TRIAL USE ONLY

NALTREXONE/GABAPENTIN/PLACEBO

STORAGE: Don't store medication above 25°C.

KEEP OUT OF REACH OF CHILDREN AND PETS.

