4.5 QUALITY ASSURANCE

Informed consent quality assurance

The RA will review Informed Consent Forms (ICFs) for completeness with the participant present. Items to check will include, but are not limited to: responses/initials collected for all questions, correct version of ICF used, signed and dated by both subject and RA. Both the RA and project manager will review ICFs weekly for completeness.

Assessment quality assurance

During the assessment, if the participant provides conflicting answers or answers that did not make logical sense (either within the same section or between sections), the RA will gently try to help the participant arrive at more logical answers. However, the RA will not force the participant to change his or her answers. Certain quality assurance checks are built into the assessment. The system will flag any inappropriate responses and prevent the RA from continuing until the issue is resolved. The RA will never guess to correct a mistake. The only instance when a change can be made to the completed assessment is in the event that the RA is 100% certain that an error was made in data entry.

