6.5. UNBLINDING PROTOCOL

Participants may be unblinded if there is an urgent medical need, as determined by the clinician evaluating the participant. If a participant is unblinded, study medication may be discontinued.

The following are examples of events that may result in emergency unblinding:

- -An SAE occurs that is thought to be most likely or definitely related to the study drug.
- -An AE or SAE occurs and the clinician treating the patient concludes that knowledge of the treatment arm is necessary to determine the therapy provided to the patient.
- -The study drug is accidentally ingested by a child.

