7.3 DATA SECURITY AND CONFIDENTIALITY

Screening forms and most other research paperwork will not include the participant's name; instead, a unique ID will be assigned to each person screened, and another number assigned to those who enroll.

Tracking information will be kept similarly. Computer data will be password protected, and accessible only to research associates needing the information for follow-up purposes.

Any documents with identifiable participant data will only be accessible to the Russian Co-Investigators (Drs. [name] and [name]), the project manager, and the RAs who recruit and follow participants, and perform QC.

Boston University School of Public Health's Biostatistics and Epidemiology Data Analytics Center (BEDAC) will design, develop and maintain the electronic data collection forms, participant and data tracking, and underlying SQL database systems, and implement procedures for data quality control, including multiple checks for entered data. Electronic data collection forms will be designed to read easily, have clear instructions, preprogrammed skip patterns, real-time range checks and internal logic to minimize missing data and result in "cleaner" data at capture.

Electronic research data will be entered directly into REDCap, which is maintained on secure BU servers. All central systems are secured physically behind two card-access doors with access to the primary door restricted to key personnel. Data will be kept indefinitely. The mastercode will be kept separate from any study data.

Assessment data will be collected directly onto computers by research assessors. Use of electronic data collection will obviate the need for double data entry and limit missing data through required fields. All data will be converted to SAS datasets and reviewed for logic, skip patterns, response ranges, and internal inconsistencies. The Boston and Russian teams will work together to resolve data issues.

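### The placebo baseline line in 3.4.C gives 63 capsules where the schedule, 3.3.C and both active arms give 28; participant-level kit numbers in 3.2 are an optional further safeguard

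*Combined protocol and SAP*

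**What the plan says.** **Placebo supply.** The 3.4.C placebo list sets one capsule a day in week 1 (a 7-capsule box) and three a day in week 2 (a 21-capsule box). A few lines later it dispenses a 21-capsule and a 42-capsule box at baseline, described as 14 days of medication. Section 3.3.C gives placebo participants a 7-capsule and a 21-capsule box, as do the naltrexone and gabapentin lists in 3.4.C.

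**Naltrexone text.** The week 2 sentence in 3.3.A mentions only the daily naltrexone capsule, whereas 3.4.C adds one placebo capsule twice daily. Section 3.3.A also gives the daily number of placebo capsules in this arm as one to six.

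**Pack handling.** Under 3.2 the pharmacist is to "deliver a supply of packaged boxes of study medication labeled with the group assignment to the study team". After REDCap assigns a group, "The RA then retrieves the pack of study medication from the identified group", writes the study ID on it and enters a group number. No kit number is described, and the number of group codes per arm is not stated.

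**Blinding.** Section 3.1 states: "Study participants, investigators, staff, and physicians administering the medications will be unaware of specific group assignment". The box label as printed in 3.4.C reads "NALTREXONE/GABAPENTIN/PLACEBO", so it does not single out one drug. On emergency unblinding, 6.5 says: "Participants may be unblinded if there is an urgent medical need, as determined by the clinician evaluating the participant". It does not say who else may receive the result.

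**Role of the research assessors (RAs).** Section 7.3: "Assessment data will be collected directly onto computers by research assessors". They also review symptoms at each visit (6.2) and count leftover capsules (3.4.B).

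**The concern.** Section 3.4.C is the operational dispensing list, the part of the protocol a pharmacist or packager would work from. A placebo line that departs from both active arms at the first dispensing matters for two reasons.

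- **Masking.** Placebo packs would have no 7-capsule box and would include a 42-capsule box that the active arms do not receive at baseline. All study staff are trained on the protocol (section 10), so anyone who knew this line could recognise the pattern.
- **Dose and adherence data.** Capsule counts are one of the adherence measures in 3.4.B, and they depend on knowing how many capsules were handed out. A participant who took one box per week would also take more capsules than scheduled.

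The kit-number point is separate and smaller. If everyone in an arm shares one code, revealing that code for one participant reveals it for all of them. The RAs who handle the packs also record the Brief Pain Inventory and adverse events. When answers conflict, "the RA will gently try to help the participant arrive at more logical answers", so an interviewer who knew the arm would have some room, even unintentionally, to influence a self-reported outcome.

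**Working it through.** **1. Capsules for the first 14 days**

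Inputs: the daily schedule and box sizes in 3.4.C and 3.3.C.

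- Need: 7 × 1 + 7 × 3 = 7 + 21 = 28.
- Active arms, 3.4.C: 7 + 21 = 28. Agrees.
- Placebo, 3.3.C: 7 + 21 = 28. Agrees.
- Placebo, 3.4.C: 21 + 42 = 63. Does not agree; the stated 14 days cannot be reproduced.
- Excess: 63 − 28 = 35 per participant (63/28 = 2.25 times the need). Over 15 placebo participants: 15 × 35 = 525.

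**2. Eight-week total**

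- By daily schedule: 7 + 21 + (35 × 6) + (4 × 6 + 3 × 3) = 7 + 21 + 210 + 33 = 271.
- By boxes, active arms and 3.3.C: 28 + 42 + 84 + 84 + 33 = 271. Agrees.
- By boxes, 3.4.C placebo list: 63 + 42 + 84 + 84 + 33 = 306. Excess 35/271 = 12.9%.

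Only the placebo baseline line fails to reconcile.

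**3. Consequences if that line were followed**

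- Taken one box per week: 21/7 = 3 a day, then 42/7 = 6 a day, instead of 1 and then 3.
- A fully adherent participant uses 28 of the baseline 63 and has 35 left. Section 3.4.B gives no adherence formula. If capsules used are divided by capsules dispensed, the result is 28/63 = 44%. If the analyst assumes 28 were dispensed, the count gives 28 − 35 = −7 taken, which is impossible.

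**4. Naltrexone arm**

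Placebo capsules per day equal total capsules minus the one naltrexone capsule:

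| Period | Total per day | Placebo per day |
|---|---|---|
| Week 1 | 1 | 0 |
| Week 2 | 3 | 2 |
| Weeks 3–7 | 6 | 5 |
| Week 8, days 1–4 | 6 | 5 |
| Week 8, days 5–7 | 3 | 2 |

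The range is zero to five. The week 2 wording in 3.3.A accounts for 7 × 1 = 7 of the 21 capsules in that box.

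**5. Reach of one code break**

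Inputs: 15 per arm and 13 expected to complete week 8 (2.7.A). The number of codes per arm is an assumption, shown over a range.

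| Codes per arm | Participants sharing the broken code | Others sharing it | Of those, expected to complete week 8 (× 13/15) |
|---|---|---|---|
| 1 | 15 | 14 | 12.1 |
| 2 | 7.5 | 6.5 | 5.6 |
| 3 | 5 | 4 | 3.5 |
| Kit number per participant | 1 | 0 | 0 |

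These are upper bounds, because records for anyone already past week 8 are unaffected for the primary outcome. The documents give no rate of code breaks, so no probability is attached.

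**The case against.** **On the placebo line.** The rest of the protocol already contradicts it: its own list defines a 7-capsule box for week 1 and a 21-capsule box for week 2, its 14-day description fits only 28 capsules, and 3.3.C has the right boxes. A careful pharmacist would notice. Staff trained on the protocol would also read 3.3.C. This stands: the line is most likely a slip, and 525 capsules measures the size of the slip, not harm done. It does not remove the need for correction, because the protocol leaves two incompatible dispensing instructions and one of them would distinguish an entire arm.

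**On kit numbers.** Harm requires four steps that the documents do not show: one code per arm, a code break, the result reaching the RAs, and an RA then influencing a score that a still-masked participant reports. Several passages weaken the chain. Section 4.5 says RAs do not force a change of answer and never guess to correct a mistake. Section 6.2 gives decisions on serious and severe adverse events to designated persons, and 6.3.A does the same for relatedness and medication changes for other events. The first unblinding example in 6.5 is a drug-related serious event, so a break would probably be handled above the RAs. This largely stands. What remains is that the text does not exclude the RAs: the decision lies with the evaluating clinician, and "Research Assessors in this study are all trained addiction psychiatrists". Shared group stock is also a workable choice for a 45-person pilot aimed at estimation, so kit numbers are an improvement, not a correction of an error.

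**A stronger reading to avoid.** A reader might infer from the group-labelled boxes that the RAs can see the arm. The documents do not support this. Blinding of staff is stated in 2.3, 3.1 and 3.2, doses are to look identical (3.3), a group number suggests a code, and the printed label carries all three drug names.

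**Conclusion.** The placebo baseline line in 3.4.C is wrong as written: 63 capsules where 28 are required, 35 too many per participant. This follows from the protocol's own schedule and needs no outside assumption. That it would affect masking or adherence data is conditional on packaging or dispensing having followed the line, and nothing in the documents shows that it did. The two points in 3.3.A are text clean-up.

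The absence of a participant-level kit number in 3.2 is a secondary matter on which change is optional. The figure of up to 15 participants exposed by one break assumes a single code per arm and a result that reaches the RAs. With two or three codes per arm it falls to 7 or 8, or to 5. Neither the chance of a break nor the size of any resulting bias can be estimated from the documents.

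**What to change.** **Needed (text only).**

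- 3.4.C, placebo list: replace the baseline boxes with one of 7 and one of 21 capsules, 28 in total, matching the active arms. Confirm that the compounding pharmacy's packing instructions agree.
- 3.3.A: add one placebo capsule twice daily to week 2, and change the daily placebo range to zero to five.

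**Optional.**

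- 3.2: label packs with a unique kit number per participant, have REDCap return only that number, and drop the group label and the group-number entry. Add the kit number to the label contents in 3.4.C. Keep the kit-to-arm list with the pharmacist or an unblinded statistician.
- 6.5: state that an unblinding result goes only to the treating clinician where possible, and not to RAs who assess participants.
- If group codes are kept, state how many there are per arm.

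**Cost.** The optional part needs a kit list for 45 participants and numbers on about 360 boxes (2 + 1 + 2 + 2 + 1 = 8 boxes each, × 45). The main downside is a few spare kits per arm, because lost or stolen medication (3.4.D) could no longer be replaced from shared stock. Sample size, power and visits do not change.
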